# 3.3.3 Responsibility of the HPV Vaccine Program Pathology Panel

The HPV Vaccine Program Pathology Panel will be responsible for providing the definitive pathologic diagnoses of cervical biopsies, vaginal biopsies, external genital lesion biopsies, endocervical curettage, and cervical definitive therapy specimens for study purposes (not for medical management). Cervical histology slides and slides from external genital lesion biopsies and vaginal lesion biopsies will be evaluated by HPV Vaccine Program Pathology Panel. The HPV Vaccine Program Pathology Panel will prepare reports on each tissue specimen. A separate guideline that details the HPV Vaccine Program Pathology Panel process has been approved by the HPV Vaccine Program Pathology Panel.

# **3.4 SAFETY MEASUREMENTS**

# 3.4.1 Clinical and Laboratory Measurements for Safety

Serious adverse experiences will be reported as described in Section 3.4.5.

Pregnancy and infant information will be reported as described in Section 3.4.4.

# **3.4.2 Recording Adverse Experiences**

An adverse experience is defined as any unfavorable and unintended change in the structure, function, or chemistry of the body temporally associated with the use of the SPONSOR's product, whether or not considered related to the use of the product. Any worsening (i.e., any clinically significant adverse change in frequency and/or intensity) of a preexisting condition which is temporally associated with the use of the SPONSOR's product, is also an adverse experience.

67

Changes resulting from normal growth and development which do not vary significantly in frequency or severity from expected levels are not to be considered adverse experiences. Examples of this may include, but are not limited to, teething, typical crying in infants and children, and onset of menses or menopause occurring at a physiologically appropriate time.

All adverse experiences will be collected from the time the consent form is signed through 14 days following the first vaccination(s) and from the time of any subsequent vaccination(s) through 14 days thereafter, and such events will be recorded at each examination on the Adverse Experience Case Report Forms/Worksheets.

Serious adverse experiences occurring outside of that time period will be reported as described in Section 3.5.

# **3.4.3 Definition of an Overdose for This Protocol**

No overdose should occur since no subject will be administered vaccinations of 9-valent HPV L1 VLP vaccine during this study.

# 3.4.4 Reporting of Pregnancy/Breastfeeding Events to the SPONSOR

Although not considered an adverse experience, it is the responsibility of the investigators or their designees to report any pregnancy in a subject (spontaneously reported to them or detected by urine or serum pregnancy test per protocol).

All randomized subjects who receive study vaccine, including discontinued subjects who agree to provide further information, must be followed to the completion/termination of the pregnancy. In addition, if the pregnancy continues to term, the outcome (health of the infant) must be reported.

Infant serious adverse experiences (SAEs) for all infants born to subjects who received study vaccine must be reported to the SPONSOR.

The reporting of pregnancy and infant SAE events must be reported within 24 hours to the SPONSOR either by electronic media or paper. Refer to Data Entry Guidelines (DEGs) for instructions for what information must be reported.

68

# 3.4.5 Immediate Reporting of Adverse Experiences to the SPONSOR

## **3.4.5.1 Serious Adverse Experiences**

Any serious adverse experience brought to the attention of an investigator who is a qualified physician at any time also must be reported immediately to one of the individuals listed on the sponsor contact information page (found in the administrative binder) if the event is either:

1. A death which resulted in the subject/patient discontinuing the study

or

2. A serious adverse experience that is considered by an investigator who is a qualified physician to be possibly, probably, or definitely vaccine related.

or

3. A serious adverse experience that is considered by an investigator who is a qualified physician to be possibly, probably, or definitely related to a study procedure.

All subject/patients with serious adverse experiences must be followed up for outcome.

# 3.4.6 Evaluating Adverse Experiences

Refer to Table 3-4 for instructions in evaluating adverse experiences.

# Product: V503 Protocol/Amendment No.: 002-20

69

#### Table 3-4

An investigator who is a qualified physician, will evaluate all adverse experiences as to:

Maximum	Mild	awareness of sign or symptom, but easily tolerated (for pediatric studies, awareness of symptom, but easily tolerated)			
Intensity	Moderate	discomfort enough to cause interference with usual activity (for pediatric studies, definitely acting like something is wrong)			
2	Severe	incapacitating with inability to work or do usual activity (for pediatric studies, extremely distressed or unable to do usual activities) Injection site redness or			
	swelling from the day of vaccination through Day 4 post-vacc will be evaluated by maximum size.				
Seriousness	A serious advers	e experience is any adverse experience occurring at any dose that:			
	†Results in death ; or				
		ing; or places the subject/patient, in the view of the investigator, at immediate risk of death from the experience as it occurred [Note: This does not include an ice that, had it occurred in a more severe form, might have caused death.]; or			
		ersistent or significant disability/incapacity (substantial disruption of one's ability to conduct normal life functions); or			
	†Results in or p precautionary m	Results in or prolongs an existing inpatient hospitalization (hospitalization is defined as an inpatient admission, regardless of length of stay, even if the hospitalization is a recautionary measure for continued observation. (Note: Hospitalization [including hospitalization for an elective procedure] for a preexisting condition which has not worsened oes not constitute a serious adverse experience.); or			
	†Is a congenital anomaly/birth defect (in offspring of subject/patient taking the product regardless of time to diagnosis);or				
	Is a cancer; or				
	Is an overdose (Whether accidental or intentional.) Any overdose whether or not associated with an adverse experience must be reported within 24 hours to one of the individuals on the Contact Information Page found in the Administrative Binder.				
	Other important medical events that may not result in death, not be life threatening, or not require hospitalization may be considered a serious adverse experience when, based upon appropriate medical judgment, the event may jeopardize the subject/patient and may require medical or surgical intervention to prevent one of the outcomes listed previously (designated above by a + ).				
Duration		d the start and stop dates of the adverse experience. If less than 1 day, indicate the appropriate length of time and units			
Action taken	Did the adverse experience cause the test vaccine to be discontinued?				
Relationship to test vaccine	Did the test vaccine cause the adverse experience? The determination of the likelihood that the test vaccine caused the adverse experience will be provided by an investigator who is a qualified physician. The investigator's signed/dated initials on the source document or worksheet, that supports the causality noted on the AE form, ensures that a medically qualified assessment of causality was done. This initialed document must be retained for the required regulatory time frame. The criteria below are intended as reference guidelines to assist the investigator in assessing the likelihood of a relationship between the test vaccine and the adverse experience based upon the available information.				
		omponents are to be used to assess the relationship between the test vaccine and the AE; the greater the correlation with the components and their			
	respective elements (in number and/or intensity), the more likely the test vaccine caused the adverse experience (AE):				
	Exposure	Is there evidence that the subject/patient was actually exposed to the test vaccine such as: reliable history, acceptable compliance assessment (e.g. diary), seroconversion or identification of vaccine virus in bodily specimen?			
	Time Course	Did the AE follow in a reasonable temporal sequence from administration of the test vaccine? Is the time of onset of the AE compatible with a vaccine-induced effect?			

V503\_002-20\_ASSEM\_PROT\_Full\_Prot APPROVED — 06-Sep-2012

U.S. IND, U.S. Study

Restricted Sconfidential – Limited Access

# Product: V503 Protocol/Amendment No.: 002-20

Relationship	The following components are to be used to assess the relationship between the test vaccine and the AE: (continued)		
to test vaccine			
(continued)			
	Rechallenge	Was the subject/patient reexposed to the test vaccine in this study?	
		If yes, did the AE recur or worsen?	
		If yes, this is a positive rechallenge. If no, this is a negative rechallenge.	
		(Note: This criterion is not applicable if: (1) the initial AE resulted in death or permanent disability, or (2) the study is a single-dose vaccine study.)	
		NOTE: IF A RECHALLENGE IS PLANNED FOR AN ADVERSE EVENT WHICH WAS SERIOUS AND WHICH MAY HAVE BEEN CAUSED BY	
		THE TEST VACCINE, OR IF REEXPOSURE TO THE TEST VACCINE POSES ADDITIONAL POTENTIAL SIGNIFICANT RISK TO THE	
		SUBJECT/PATIENT, THEN THE RECHALLENGE MUST BE APPROVED IN ADVANCE BY THE U.S. CLINICAL MONITOR AND THE	
	INSTITUTIONAL REVIEW BOARD/INDEPENDENT ETHICS COMMITTEE.		
	Consistency	Is the clinical/pathological presentation of the AE consistent with previous knowledge regarding the test vaccine or vaccine class pharmacology or	
	with Study Vaccine Profile	toxicology?	
		relationship will be reported on the case report forms /worksheets by an investigator who is a qualified physician according to his/her best clinical judgment,	
		ation of the above elements.	
	Ŭ		
	Use the following scale of criteria as guidance (not all criteria must be present to be indicative of a vaccine relationship).DefinitelyThere is evidence of exposure to the test vaccine. The temporal sequence of the AE onset relative to administration of the test vaccine is reasonable.		
	related	is more likely explained by the test vaccine than by another cause. Dechallenge is positive. Rechallenge (if feasible) is positive. The AE shows a pattern	
	related	consistent with previous knowledge of the test vaccine or test vaccine class.	
	Probably	There is evidence of exposure to the test vaccine. The temporal sequence of the AE onset relative to administration of the test vaccine is reasonable. The AE	
	related	is more likely explained by the test vaccine than by another cause. Dechallenge (if performed) is positive.	
	Possibly related	There is evidence of exposure to the test vaccine. The temporal sequence of the AE onset relative to administration of the test vaccine is reasonable. The AE	
		could have been due to another equally likely cause. Dechallenge (if performed) is positive.	
	Probably not	There is evidence of exposure to the test vaccine. There is another more likely cause of the AE. Dechallenge (if performed) is negative or ambiguous.	
	related	Rechallenge (if performed) is negative or ambiguous.	
	Definitely not	The subject/patient did not receive the test vaccine. OR Temporal sequence of the AE onset relative to administration of the test vaccine is not reasonable.	
	related	OR There is another obvious cause of the AE.	

Restricted Sconfidential – Limited Access

# 3.4.7 SPONSOR Responsibility for Reporting Adverse Experiences

All adverse experiences will be reported to regulatory agencies, IRB/IECs, and investigators in accordance with all applicable global laws and regulations.

71

# 3.5 DATA ANALYSIS

This section outlines the statistical analysis strategy and procedures for the study. If changes are made after the start of the study to the statistical analysis plan presented in the Data Analysis section of this protocol extension, the changes will be described in the Clinical Study Report for the study, as appropriate. Post hoc exploratory analyses will be clearly identified in the CSR. No separate Statistical Analysis Plan (SAP) will be issued for this study.

### 3.5.1 Responsibility for Analyses/In-House Blinding

The statistical analysis of the data obtained from this study will be the responsibility of the Clinical Biostatistics department of the SPONSOR.

This extension of Protocol 002 will not be blinded, because all participants will have received 9-valent HPV L1 VLP vaccine. Freezes of the clinical database will be executed for each of the interim analyses at Months 72 and 96 and at end-of-study. Prior to each data freeze, the clinical data will be reviewed, cleaned, and screened to ensure accuracy and completeness following the SPONSOR's Global Development Processes (GDP) relating to Data Management. The data will be reviewed and errors will be corrected and protocol violations have been reviewed prior to freezing the clinical database for immunogenicity, safety, and effectiveness analyses.

The first analysis conducted under Protocol 002-20 is planned to take place at Month 72. During this interim analysis, safety, immunogenicity, and effectiveness data will be analyzed and feasibility of continuing the study through Month 126 will be assessed. If study continues beyond Month 72, additional analyses of safety, immunogenicity and effectiveness are planned to include data through Month 96 and Month 126.

# 3.5.2 Hypotheses/Estimation

There are no hypotheses for this long term follow-up study.

# 3.5.3 Analysis Endpoints

#### **3.5.3.1 Immunogenicity Endpoints**

Immunogenicity endpoints are GMTs and seropositivity rates to HPV 6, 11, 16, 18, 31, 33, 45, 52 and 58. A subject is considered seropositive for a given HPV type if he or she has a titer at or above the serostatus cutoff for that HPV type for the immunoassay considered. Serum samples are collected as indicated in flow chart in Section 1.7. Immunogenicity testing will be conducted at Months 66, 90 and 126.

#### **3.5.3.2 Safety Endpoints**

Safety endpoints are vaccine- or study procedure-related serious adverse experiences, deaths, and pregnancy- and infant-related outcomes.

#### **3.5.3.3 Effectiveness Endpoints**

Effectiveness endpoints are gender-specific. The effectiveness endpoint of primary interest is the incidence of subjects with at least one of the following endpoints (for the appropriate gender).

### **3.5.3.3.1** Female Endpoints

For females, the effectiveness endpoint of interest is the composite endpoint of persistent HPV 6, 11, 16, 18, 31, 33, 45, 52 or 58 infection and HPV 6-, 11-, 16-, 18-, 31-, 33-, 45-, 52-, or 58-related CIN, AIS, VIN, VaIN, genital warts, and cervical/vaginal/vulvar cancer.

I. Persistent infection (with a duration of 6 months):

This endpoint is defined to have occurred if a subject who, after completion of the Month 7 visit, is positive for the same HPV type by the HPV 6/11/16/18/31/33/45/52/58 PCR assay to at least 1 common gene in 2 or more consecutive cervicovaginal/external genital swab, biopsy, or definitive therapy samples obtained at two or more consecutive visits 6 months (± 1 month) or longer.

Persistent infection is defined based on the protocol visit intervals. Scheduled visits for the collection of swabs are at 6-monthly intervals, so most cases of persistent infection will be based on consecutive specimens obtained 6 months apart; however, due to protocol-allowable deviations for scheduled visit intervals, the minimum length of time between samples for a subject to be counted as a case of persistent infection will be 4 months.

If a subject has 2 consecutive samples that are PCR positive to at least one common gene for the same HPV type and at least one of the samples is a biopsy or definitive therapy sample showing pathologic evidence of HPV disease, then the subject will be considered a case of persistent infection without regard to the length of time between the samples.

II. External Genital Warts, VIN, VaIN, and/or vulvar or vaginal cancer related to HPV 6, 11, 16, 18, 31, 33, 45, 52, or 58:

A subject will be considered to have a case of external genital warts, VIN, VaIN, and/or vulvar or vaginal cancer related to HPV 6, 11, 16, 18, 31, 33, 45, 52, or 58, if she has the following:

- On an individual biopsy or excised tissue, a consensus diagnosis by the HPV Vaccine Program Pathology Panel of condyloma acuminata (genital warts), VIN 1, VIN 2, VIN 3, VaIN 1, VaIN 2, VaIN 3, or vulvar cancer or vaginal cancer AND
- Detection of HPV 6, 11, 16, 18, 31, 33, 45, 52, or 58 by Thinsection PCR in an adjacent section from the same tissue block.

III. CIN, AIS, and/or cervical cancer related to HPV 6, 11, 16, 18, 31, 33, 45, 52, or 58:

A subject will be considered to have a case of CIN, AIS, and/or cervical cancer related to HPV 6, 11, 16, 18, 31, 33, 45, 52 or 58 if she has the following:

- On an individual biopsy, ECC, LEEP, or conization (cold knife/laser) specimen, a consensus diagnosis by the HPV Vaccine Program Pathology Panel of CIN 1, CIN 2, CIN 3, AIS, or cervical cancer, AND
- Detection of HPV 6, 11, 16, 18, 31, 33, 45, 52, or 58 by Thinsection PCR in an adjacent section from the same tissue block.

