#### 2.1.2 Secondary Objectives

- (1) Co-Secondary Objective: To estimate the long-term effectiveness of 9-valent HPV L1 VLP vaccine, when administered to 9- to 15-year-old girls, with respect to the combined incidence of persistent HPV 6, 11, 16, 18, 31, 33, 45, 52, and 58 infection for a duration of 6 months (within ± 1 month windows) or longer and HPV 6, 11, 16, 18, 31, 33, 45, 52, and 58-related Cervical Intraepithelial Neoplasia (CIN), Adenocarcinoma In Situ (AIS), Vulvar Intraepithelial Neoplasia (VIN), Vaginal Intraepithelial Neoplasia (VaIN), genital warts, and cervical/vaginal/vulvar cancer.
- (2) Co-Secondary Objective: To estimate the long-term effectiveness of 9-valent HPV L1 VLP vaccine, when administered to 9- to 15-year-old boys, with respect to the combined incidence of persistent HPV 6, 11, 16, 18, 31, 33, 45, 52, and 58 infection for a duration of 6 months (within ± 1 month windows) or longer and HPV 6, 11, 16, 18, 31, 33, 45, 52, and 58-related Penile Intraepithelial Neoplasia (PIN), genital warts, and penile/perineal/perianal cancer.

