# 2.7.2 Effectiveness

At the time of the first interim analysis (Month 72), summaries of the incidence of HPV 6, 11, 16, 18, 31, 33, 45, 52, and 58 related persistent infection for a duration of  $\geq 6$  months (within  $\pm 1$  month windows) and cervical, vulvar, vaginal, perineal, perinal, and penile intraepithelial preinvasive and invasive disease, and external genital lesions will be provided, separately for males and females. Similar summaries of the incidence rates of HPV 6, 11, 16, 18, 31, 33, 45, 52, and 58-related persistent infection for a duration of  $\geq 6$  months (within  $\pm 1$  month windows) and disease will be provided to include follow-up data through the second interim analysis at Month 96 and at the end of the study at Month 126.

All subjects will contribute to the effectiveness summaries. Summaries will be provided by gender and age group (based on age at enrollment). The primary analysis group will be those who have received 3 doses of 9-valent HPV L1 VLP vaccine within one year. Subjects will be considered breakthrough cases related to a given HPV type provided they were negative to the respective HPV type by serology prior to vaccination and were sexually naïve through the 3rd dose of 9-valent HPV L1 VLP vaccine. Sexual naïveté, an inclusion criterion for the base study, is being used as a way to limit analysis of the prophylactic effect of the vaccine to subjects who were not infected prior to completion of the vaccination series. There are no PCR data from Protocol V503-002 subjects until subjects reach their 16th birthday. Therefore, the only data available to assess possible prior infection are pre-vaccination serum anti-HPV levels and sexual history. Cases in subjects with evidence of HPV exposure or infection prior to vaccination (i.e., seropositivity to the relevant HPV type(s) pre-vaccination or sexual activity prior to completion of the vaccination series) or in subjects who did not receive 3 doses of 9valent HPV L1 VLP vaccine within one year will not be considered breakthrough cases (vaccine failures). Such cases will be summarized separately.

20

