# 3.1.1.3 Epidemiology of HPV Infection and Disease

### 3.1.1.3.1 HPV Infection

The cumulative lifetime risk for HPV infection in sexually active women exceeds 50%. Available data suggest that HPV infection is also very prevalent in men [34; 35]. HPV infection is transmitted via contact with an infected individual or a contaminated object and occurs most often during sexual activity. Sixty percent (60%) of sexual partners of infected individuals develop lesions 4 weeks to 8 months after exposure [36]. HPV is often acquired immediately after sexual debut. The risk of HPV infection is strongly correlated with the number of lifetime sexual partners [37; 38]. Men and women in their late teens and early twenties are at the highest risk for HPV infection, as early sexual activity is accompanied with a higher likelihood of having new sexual partners, thus increasing the risk of exposure to the virus. The incidence of HPV infection in women increases with age during the teen years and peaks in the early 20's and declines gradually thereafter [6; 39]. In contrast, there does not appear to be such an association between HPV prevalence and age in men. This difference between genders may reflect stronger immune response to HPV in women, as suggested by findings of higher prevalence of anti-HPV antibodies in women than in men across all ages [40]. Most cervical HPV infections resolve spontaneously. On average, HPV infection persists for 4 to 20 months. However, a small proportion of infections persist beyond 1 to 2 years. Infection with HR types tends to last longer than infection with low-risk (LR) types [41; 42: 43: 44: 45].

23

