#### 3.5.3.3.2 Male Endpoints

I. Persistent infection (with duration of 6 months):

This endpoint is defined to have occurred if a subject who, after completion of the Month 7 visit, is positive for the same HPV type by the HPV 6/11/16/18/31/33/45/52/58 PCR assay to at least 1 common gene in 2 or more consecutive anogenital swab or biopsy obtained at two or more consecutive visits 6 months (± 1 month) or longer.

Persistent infection is defined based on the protocol visit intervals. Scheduled visits for the collection of swabs are at 6-monthly intervals, so most cases of persistent infection will be based on consecutive specimens obtained 6 months apart; however, due to protocol-allowable deviations for scheduled visit intervals, the minimum length of time between samples for a subject to be counted as a case of persistent infection will be 4 months.

If a subject has 2 consecutive samples that are PCR positive to at least one common gene for the same HPV type and at least one of the samples is a biopsy or definitive therapy sample showing pathologic evidence of HPV disease, then the subject will be considered a case of persistent infection without regard to the length of time between the samples.

II. External genital warts, PIN, or penile/perineal/perianal cancer related to HPV 6, 11, 16, 18, 31, 33, 45, 52 or 58:

A subject will be considered to have this endpoint if he has the following:

• Pathology panel consensus diagnosis of genital warts, PIN 1, PIN 2, PIN 3, penile, perineal, or perianal cancer, AND

74

• Detection of HPV 6, 11, 16, 18, 31, 33, 45, 52, or 58 DNA by Thinsection PCR in an adjacent section of the same tissue block.

The composite effectiveness endpoints for each gender include all of the gender-specific endpoints listed above. The incidence of each individual component will be summarized, as will the incidence of the composite endpoints for each gender. Endpoints related to non-vaccine types (i.e., HPV 35, 39, 51, 56, and 59), for the exploratory effectiveness analyses, are defined in the same way as the vaccine-type endpoints.

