#### Per-Protocol Effectiveness (PPE)

The PPE analysis population is HPV type-specific. In analyses of endpoints related to a specific HPV type (e.g., HPV 16-related endpoints) the PPE population-eligible subjects include those who:

- (1) received 3 doses of 9-valent HPV L1 VLP vaccine within 1 year; AND
- (2) were seronegative by cLIA to the specific HPV type at the time of injection of dose 1 of 9-valent HPV L1 VLP vaccine (seronegative to both types 6 and 11 in analysis of HPV 6-related, and HPV 11-related endpoints); AND
- (3) Have no other protocol violations that could interfere with the evaluation of the effectiveness of the study vaccine. Specifically, at base study Day 1, satisfied inclusion criterion 5 (i.e., " Subject must not yet have had coitarche and does not plan on becoming sexually active during the Day 1 through Month 7 period.") specified in Section 2.2 of the protocol of the base study (i.e., Protocol V503-002-00).

Inclusion criterion 5, at base study, was intended to capture subjects who had not yet been infected with HPV through sexual intercourse and were therefore likely to be HPV-naïve during the period of vaccination with 9-valent HPV L1 VLP vaccine. The seronegativity condition is another criterion intended to capture subjects who were still HPV-naïve during the period of vaccination of 9-valent HPV L1 VLP vaccine

Note that a subject can be both PPE population-eligible for analyses of endpoints related to one HPV type (e.g., HPV 16-related endpoints) and PPE population-ineligible for analyses of endpoints related to another HPV type (e.g., HPV 18-related endpoints).

In analyses of endpoints related to any vaccine HPV type (e.g., HPV 6/11/16/18/31/33/45/52/58-related endpoints), the PPE population-eligible subjects include those who are PPE population-eligible for *any of* the HPV types 6, 11, 16, 18, 31, 33, 45, 52, or 58.

Only PPE population-eligible subjects who are at least 16 years of age and have at least one follow-up visit with PCR data will contribute to the PPE analyses.

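### Persistent infections already present at a subject's first PCR swab count in a rate dated from the start of the extension, so the rate overstates incidence in observed time, most at Month 72

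*Combined protocol and SAP*

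**What the plan says.** For females, Section 3.5.3.3.1 states: "This endpoint is defined to have occurred if a subject who, after completion of the Month 7 visit, is positive for the same HPV type", at two or more consecutive visits about 6 months apart (minimum 4 months). Section 3.5.3.3.2 gives males the same post-Month 7 rule: "positive for the same HPV type by the HPV 6/11/16/18/31/33/45/52/58 PCR assay to at least 1 common gene in 2 or more consecutive anogenital swab". Neither requires a PCR-negative sample beforehand.

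Section 2.7.2 says "There are no PCR data from Protocol V503-002 subjects until subjects reach their" 16th birthday, and the flow chart in Section 1.7 starts at Month 42. It adds that "the only data available to assess possible prior infection are pre-vaccination serum anti-HPV levels and sexual history".

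The per-protocol effectiveness population (Section 3.5.4.3) requires three doses within a year, subjects who "were seronegative by cLIA to the specific HPV type at the time of injection of dose 1", and the base-study criterion "Subject must not yet have had coitarche and does not plan on becoming sexually active during the Day 1 through Month 7 period". Contributing subjects must be at least 16 with one PCR visit. The full analysis set has no condition on first-swab PCR status either.

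The co-secondary objectives (Section 2.1.2) are framed "with respect to the combined incidence of persistent HPV 6, 11, 16, 18, 31, 33, 45, 52, and 58 infection" plus related disease. Section 2.7.2 dates the cumulative rate from the start of the extension. Section 3.5.5.3 gives it per 100 person-years with exact Poisson intervals and does not restate the origin. On duration, Section 3.1.1.3.1 says: "On average, HPV infection persists for 4 to 20 months".

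**The concern.** Dose 3 was at Month 6, so the first swab comes at least 36 months later. A subject positive for HPV 16 at Months 42 and 48 is counted as a case of the extension, although the infection began in time nobody observed and that time is outside the stated follow-up. The first pair of swabs therefore collects a standing pool of longer-lasting infections on top of new ones, and no section separates the two.

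The incidence estimate is the deliverable of both co-secondary objectives. The same definition serves the non-vaccine types used to look for cross-protection, and Section 3.5.5.3 foresees descriptive comparison with Protocol V503-001. The distortion is largest at Month 72, where follow-up is shortest.

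**Working it through.** The plan states no expected incidence or case count, so there is no figure of its own to reproduce.

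**Inputs from the documents.** Swabs every 6 months; Month 42 to Month 72 is 2.5 years and to Month 126 is 7 years; mean duration D of 4 to 20 months (Section 3.1.1.3.1); in men, median clearance 5.9 to 7.5 months and a 12.2-month average for HPV 16 (Section 3.1.1.3.4).

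**Assumptions.** Exponential durations; constant acquisition after debut; cases few enough to ignore depletion; person-time from first swab; no dropout.

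**1. Steady exposure before first swab, all entering at Month 42.** The pool at first swab, in years of new detectable cases, is P = 0.5 / (1 − exp(−0.5/D)), D in years. A new infection needs two positive visits, so new cases confirmable by the cutoff cover 2.0 years of detections by Month 72 and 6.5 by Month 126. The share already present is P/(P + 2.0) and P/(P + 6.5). The planned rate relative to the true detectable rate is (P + 2.0)/2.5 and (P + 6.5)/7.

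| Mean D (months) | P | Share, Month 72 | Share, Month 126 | Planned rate, true = 1 |
|---|---|---|---|---|
| 4 | 0.64 | 24% | 9% | 1.06 to 1.02 (−3.5%) |
| 12 | 1.27 | 39% | 16% | 1.31 to 1.11 (−15%) |
| 20 | 1.93 | 49% | 23% | 1.57 to 1.20 (−23%) |

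For men, medians of 5.9 and 7.5 months give means of 5.9/0.693 = 8.5 and 7.5/0.693 = 10.8. With these and 12.2 months, P = 0.99, 1.17 and 1.29; shares are 33%, 37% and 39% at Month 72 and 13%, 15% and 17% at Month 126. The 20-month row should not be applied to men.

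**2. Less prior exposure.** After T years of exposure, the first swab pair yields (1 − exp(−T/D)) / (1 − exp(−0.5/D)) times the cases of a later interval. At T = 0.5 this is 1, the pool is worth 0.5 years, and (0.5 + 2.0)/2.5 = 1: no drift.

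**3. The protocol calendar.** I averaged these expressions over ages spread evenly from 9 to under 16 at Day 1, with no exposure before Month 7, first swab at the first visit at age 16 or older from Month 42, and debut age normal with SD 1.5 years. Acquisition is 0.5 per 100 person-years after debut. These values are assumptions. Rates are cumulative per 100 person-years, Month 72 to Month 126; (b) is defined in step 4.

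| Mean debut (y) | D (months) | Share, M72 / M126 | Planned rate | Rate (b) |
|---|---|---|---|---|
| 15.5 | 4 | 25% / 8% | 0.055 to 0.056 (+2%) | 0.054 to 0.056 (+4%) |
| 15.5 | 12 | 36% / 12% | 0.261 to 0.241 (−8%) | 0.222 to 0.230 (+4%) |
| 15.5 | 20 | 41% / 15% | 0.380 to 0.333 (−12%) | 0.298 to 0.309 (+4%) |
| 17 | 4 | 20% / 5% | 0.042 to 0.049 (+17%) | 0.044 to 0.050 (+14%) |
| 17 | 12 | 28% / 8% | 0.189 to 0.206 (+9%) | 0.181 to 0.208 (+15%) |
| 17 | 20 | 31% / 9% | 0.266 to 0.280 (+5%) | 0.242 to 0.278 (+15%) |
| 18.5 | 4 | 14% / 3% | 0.025 to 0.038 (+53%) | 0.028 to 0.041 (+43%) |
| 18.5 | 12 | 19% / 4% | 0.107 to 0.158 (+47%) | 0.115 to 0.166 (+44%) |
| 18.5 | 20 | 21% / 4% | 0.147 to 0.213 (+45%) | 0.154 to 0.223 (+45%) |

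On the same person-time, the planned rate is 1/(1 − share) times the rate of infections that began under observation: 1/(1 − 0.14) = 1.16 to 1/(1 − 0.49) = 1.96 at Month 72, and 1.03 to 1.30 at Month 126.

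**4. Where person-time for the split rate should start.** A subject negative at first visit cannot be a swab-confirmed case before the third visit. Counting person-time from first swab gives 2.0/2.5 = 0.80 and 6.5/7 = 0.93 under constant risk, a spurious rise of 16%. Starting at the second PCR visit gives 2.0/2.0 and 6.5/6.5, which is flat. That is rate (b).

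**5. Masking.** In a simulation with debut at 15.5, 20-month duration and a 1.2-fold rise in acquisition after Month 72, the planned cumulative rate at Months 72, 96 and 126 was 0.378, 0.365 and 0.371, which looks stable. With a 1.5-fold rise it went 0.394, 0.414, 0.440, so the rise shows.

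**The case against.** These are genuine infections after vaccination, which is what the plan means to count. That stands. A reader might infer that they reflect infection before vaccination and should be dropped; the serology and sexual-history conditions give no ground for that. What is unknown is when they began.

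A reader might also infer that the planned rate will fall and so hide waning. The documents do not support that as a general result. Subjects were sexually naive at Day 1, and Section 3.1.1.3.1 says incidence in women rises through the teens and peaks in the early twenties. In step 3, a fall appears only with early debut and longer durations; with later debut the rate rises. The plan also tests no hypothesis and specifies no waning comparison.

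An unconfirmable half-year in the planned denominator partly offsets the pool. Against (b), the planned Month 72 rate is 57% higher at most and is slightly lower with debut at 18.5.

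The time-to-event plots (if more than 5 cases) and the exploratory case descriptions might reveal clustering at the first visit pair, but neither yields a rate. Precision may be poor: with an assumed 10 cases, the exact interval is 4.8 to 18.4, or −52% to +84%. That limits any reading of drift; it does not make the numerator right.

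**Conclusion.** The concern holds as a mixing of infections of unknown onset with new ones in a rate reported as incidence. That follows from the text alone. Its size rests on assumed debut ages, an assumed even age spread and exponential durations: about 14% to 41% of cases through Month 72 on the protocol calendar, up to 49% with steady prior exposure, and 3% to 23% through Month 126. Masking is plausible for modest waning with early debut and long durations, and was not seen with a 1.5-fold rise.

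A reader might take (b) as a waning measure. It is not: under constant post-debut risk it still rises 4% to 45% in step 3, because more subjects become sexually active.

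**What to change.** In Sections 3.5.3.3 and 3.5.5.3, keep the all-case composite as planned and add, by type:

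- (a) the number and proportion of subjects PCR-positive for that type at their first PCR visit who go on to meet the definition, labelled as breakthrough of unknown onset;
- (b) the rate per 100 person-years in subjects PCR-negative for that type at first PCR visit, with person-time starting at the second PCR visit.

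Use (b) as the estimate of incidence in observed time. State that changes in either rate across Months 72, 96 and 126 are not evidence of waning or of its absence. Say how (b) treats a case met through a diseased biopsy, since that route has no minimum interval and can precede the third visit. State where person-time starts for the composite, particularly for subjects under 16 at Month 42. Any sizing for males should use the durations in Section 3.1.1.3.4.

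The cost is wording and one split in the tables; no new data are needed. The downside is that (b) has fewer cases and a wider interval than the pooled rate.
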